7.3.2.1 Suspected

A suspected adverse reaction is defined as any adverse event for which there is a reasonable possibility that the drug caused the adverse event. For the purposes of IND safety reporting, "reasonable possibility" indicates that there is evidence to suggest a causal relationship between the drug and the adverse event. A suspected adverse reaction implies a lesser degree of certainty about causality than an adverse reaction.

7.3.2.2 Unexpected

An adverse event or suspected adverse reaction is considered *unexpected* if it is not listed in the investigator brochure or package insert(s), or is not listed at the specificity or severity that has been observed, or, if an investigator brochure is not required or available, is not consistent with the risk information described in the general investigational plan or elsewhere in the current application.

“Unexpected,” as used in this definition, also refers to adverse events or suspected adverse reactions that are mentioned in the investigator brochure as occurring with a class of drugs or as anticipated from the pharmacological properties of the drug, but are not specifically mentioned as occurring with the particular drug under investigation.

Adverse events that would be anticipated to occur as part of the disease process are considered *unexpected* for the purposes of reporting because they would not be listed in the investigator brochure. For example, a certain number of non-acute deaths in a cancer trial would be anticipated as an outcome of the underlying disease, but such deaths would generally not be listed as a suspected adverse reaction in the investigator brochure.

7.3.2.3 Serious

An adverse event or suspected adverse reaction is considered *serious* if, in the view of either the investigator or sponsor, it results in any of the following outcomes:

- Death
- Life-threatening adverse event
- Inpatient hospitalization or prolongation of existing hospitalization
- A persistent or significant incapacity or substantial disruption of the ability to conduct normal life function
- Congenital anomaly/birth defect

Important medical events that may not result in death, are life-threatening, or require hospitalization may be considered serious when, based upon appropriate medical judgment, they may jeopardize the patient or subject and may require medical or surgical intervention to prevent one of the outcomes listed in this definition. Examples of such medical events include allergic bronchospasm requiring intensive treatment in an emergency room or at home, blood dyscrasias or convulsions that do not result in inpatient hospitalization, or the development of drug dependency or drug abuse.

7.3.2.4 Life-threatening

An adverse event or suspected adverse reaction is considered *life-threatening* if, in the view of either the investigator or sponsor, its occurrence places the patient or subject at immediate risk of death. It does not include an adverse event or suspected adverse reaction that, had it occurred in a more severe form, might have caused death.

7.4 Recording of an Adverse Event

All grade 3 and above adverse events will be recorded using the NCI CTCAE v4.0. The Investigator will assign attribution of the possible association of the event with use of the investigational drug.

Relationship	Attribution	Description
Unrelated to investigational drug/intervention	Unrelated	The AE is clearly NOT related to the intervention
	Unlikely	The AE is doubtfully related to the intervention
Related to investigational drug/intervention	Possible	The AE may be related to the intervention
	Probable	The AE is likely related to the intervention
	Definite	The AE is clearly related to the intervention

Signs or symptoms reported as adverse events will be graded and recorded by the Investigator according to the CTCAE. When specific adverse events are not listed in the CTCAE they will be graded by the Investigator as *none, mild, moderate* or *severe* according to the following grades and definitions:

Grade 0	No AE (or within normal limits)
Grade 1	Mild; asymptomatic or mild symptoms; clinical or diagnostic observations only; intervention not indicated
Grade 2	Moderate; minimal, local, or noninvasive intervention (e.g., packing, cautery) indicated; limiting age-appropriate instrumental activities of daily living (ADL)
Grade 3:	Severe or medically significant but not immediately life-threatening; hospitalization or prolongation of hospitalization indicated; disabling; limiting self-care ADL
Grade 4:	Life-threatening consequences; urgent intervention indicated
Grade 5:	Death related to AE

7.5 Follow-up of Adverse Events

All adverse events will be followed with appropriate medical management until resolved. Patients removed from study for unacceptable adverse events will be followed until resolution or stabilization of the adverse event. For selected adverse events for which administration of the investigational drug was stopped, a re-challenge of the subject with the investigational drug may be conducted if considered both safe and ethical by the Investigator.

7.6 Expedited Reporting

Reporting to the Data and Safety Monitoring Committee

If a death occurs during the treatment phase of the study or within 30 days after the last administration of the study drug(s) and it is determined to be related either to the study drug(s) or to a study procedure, the Investigator or his/her designee must notify the DSMC Chair (or

qualified alternate) within 1 business day of knowledge of the event. The contact may be by phone or e-mail.

Data and Safety Monitoring Committee Contacts

DSMC Chair:	[REDACTED]	DSMC Monitors
Phone:	[REDACTED]	[name]
Email:	[REDACTED]	UCSF Helen Diller Family
Address:	[name]	Comprehensive Cancer Center
	[name]	[name]

Reporting to UCSF Committee on Human Research (Institutional Review Board)

The Principal Investigator must report events meeting the UCSF CHR definition of "Unanticipated Problem" (UP) and the San Francisco VA Medical Center within 5 business days of his/her awareness of the event.

Expedited Reporting to the Food and Drug Administration

If the study is being conducted under an IND, the Sponsor-Investigator is responsible for determining whether or not the suspected adverse reaction meets the criteria for expedited reporting in accordance with Federal Regulations (21 CFR §312.32).

The Investigator must report in an IND safety report any suspected adverse reaction that is both serious and unexpected. The Sponsor-Investigator needs to ensure that the event meets all three definitions:

- Suspected adverse reaction (as defined in 6.1.30)
- Unexpected (as defined in 0)
- Serious (as defined in 6.1.5)

If the adverse event does not meet all three of the definitions, it should not be submitted as an expedited IND safety report.

The timeline for submitting an IND safety report to FDA is no later than **15 calendar days** after the Investigator determines that the suspected adverse reaction qualifies for reporting (21 CFR 312.32(c)(1)).

Any unexpected fatal or life-threatening suspected adverse reaction will be reported to FDA no later than **7 calendar days** after the Investigator's initial receipt of the information (21 CFR 312.32(c)(2)).

Any relevant additional information that pertains to a previously submitted IND safety report will be submitted to FDA as a Follow-up IND Safety Report without delay, as soon as the information is available (21 CFR 312.32(d)(2)).

8 Statistical Considerations and Evaluation of Results

8.1 Study Endpoints

Detection rate stratified by PSA level.

8.1.1 Randomization

There will be no randomization performed.

8.2 Determination of Sample Size and Accrual Rate

8.2.1 Sample Size and Power Estimate

1,000 patients will be enrolled as part of this study over two years.

8.2.2 Accrual estimates

We estimate that roughly 500 patients with prostate cancer will be enrolled in this trial per year. Over a two-year period, this will result in up to 1000 patients being enrolled in the study.

8.3 Analyses Plans

8.3.1 Analysis of Primary Endpoints

Based on local reads for the detection of metastatic disease, the rate of localization abnormal focus of radiotracer will be stratified based upon the PSA prior to imaging.

9 Study Management

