NCT# 03803475

Gallium-68 PSMA-11 PET in prostate cancer patients

[figure not shown]
Study Drug: Gallium-68 PSMA-11

Version: 1.3

Version Date: November 26, 2019

Principal Investigator (Sponsor-Investigator)

[name]
University of California San Francisco

Revision History

Version 1.0	10/06/2018
Version 1.1	03/04/2019
Version 1.2	04/02/2019

Protocol Signature Page

Protocol No.: 185513

Version Date: 26NOV2019

1. I agree to follow this protocol version as approved by the UCSF Protocol Review Committee (PRC), Committee on Human Research (CHR), and Data Safety Monitoring Committee (DSMC).
2. I will conduct the study in accordance with applicable CHR requirements, Federal regulations, and state and local laws to maintain the protection of the rights and welfare of study participants.
3. I certify that I, and the study staff, have received the requisite training to conduct this research protocol.
4. I have read and understand the information in the Investigators' Brochure (or Manufacturer's Brochure) regarding the risks and potential benefits. I agree to conduct the protocol in accordance with Good Clinical Practices (ICH-GCP), the applicable ethical principles, the Statement of Investigator (Form FDA 1572), and with local regulatory requirements. In accordance with the FDA Modernization Act, I will ensure the registration of the trial on the www.clinicaltrials.gov website.
5. I agree to maintain adequate and accurate records in accordance with CHR policies, Federal, state and local laws and regulations.

UCSF Principal Investigator / Study Chair

Printed Name

Signature

Date

Abstract

Title	Gallium-68 PSMA-11 PET in prostate cancer patients
Patient population	Patients with biopsy proven prostate cancer who have a concern for metastatic disease.
Rationale for Study	Gallium-68 PSMA-11 has been shown to have a higher sensitivity for the detection of metastatic prostate cancer than conventional imaging.
Primary Objective	Determine detection rate of PSMA-11 PET broken down by PSA
Study Design	This is a single center open label study.
Number of patients	Total population of patients will be 1,000 patients.
Duration of Therapy	The study will involve a single imaging study.
Duration of Follow up	No follow-up will be performed.
Duration of study	The study will reach completion two years from the time the study opens to accrual.
Study Drugs	Gallium-68 labeled PSMA-11 (PSMA-HBED-CC)
Safety Assessments	The patients will also be asked to report adverse events.

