2.1 Primary

- Sensitivity on a per-patient and per-region-basis (Table 1) of ⁶⁸Ga-PSMA-11 PET for detection of tumor location confirmed by histopathology/biopsy, clinical and conventional imaging follow-up.

3 Study Design

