3.3.1 Inclusion Criteria

1. Male, age \geq 18.
2. Histopathologically proven prostate adenocarcinoma.
3. Concern for metastatic disease in one of the following settings:
 - a. Initial staging with intermediate to high risk prostate cancer.
 - b. Biochemical recurrence after initial therapy.
4. Ability to understand a written informed consent document, and the willingness to sign it.

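### Section 8.3.1 does not say whether a focus in the prostate counts, so in initial-staging patients the known primary tumour can score as a detection

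*Combined protocol and SAP*

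**What the plan says.** The whole primary analysis is one sentence in Section 8.3.1. It opens "Based on local reads for the detection of metastatic disease" and then names what is counted: "the rate of localization abnormal focus of radiotracer will be stratified based upon the PSA prior to imaging". It does not define a positive scan, does not say whether a focus in the prostate or prostate bed counts, and uses PSA as the only stratifier.

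The other statements of the endpoint do not settle the matter. Section 8.1 has "Detection rate stratified by PSA level" and the Abstract has "Determine detection rate of PSMA-11 PET broken down by PSA"; neither says what is detected. Section 2.1 gives the primary objective as per-patient and per-region sensitivity "for detection of tumor location confirmed by histopathology/biopsy, clinical and conventional imaging follow-up", which is not limited to metastases. Its regions are in a Table 1 that is not in the text available to me, and I draw nothing from that. Section 8 contains no per-region analysis.

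On the population, Section 3.3.1 requires "Histopathologically proven prostate adenocarcinoma" of everyone (criterion 2). It then admits two settings in which metastasis is a concern: "Initial staging with intermediate to high risk prostate cancer" (criterion 3a) and biochemical recurrence after initial therapy (criterion 3b). No analysis separates the two.

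**The concern.** The two halves of the sentence in Section 8.3.1 point to different events. The read is directed at metastases, while the count is of abnormal tracer foci with no site attached. In a man being staged before treatment, the tumour that qualified him for the study is expected to be in the prostate and can itself be such a focus. If it counts, the entry criterion supplies the event, and a scan showing only the primary is scored the same as one showing bone metastases.

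Two things are at stake. First, the 3a rate would say little about metastatic disease, which is the reason these men are scanned. Second, because 3a and 3b are not separated, the rate in each PSA stratum would move with the share of staging patients in it.

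Nothing later in the study would repair this. Section 3.4 provides no follow-up, and Appendix 1 lists no confirmatory assessment. If the site of each focus is not recorded at the local read, prostate-only positives could be separated afterwards only by re-reading up to 1,000 scans. Section 1.1 intends the data for pooling across institutions, so an undefined numerator would carry over.

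**Working it through.** **The plan's own figure.** Section 8.2.2: 500 patients per year × 2 years = 1,000, as stated. The point does not depend on it. The plan gives no target rate, precision or power, so there is no sample-size calculation to check.

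**Inputs for the illustration**
- *s*: share of staging patients (3a) in a stratum. Not in the documents; assumed 0 to 0.7.
- *v*: probability that the primary is visible in a staging patient. Assumed 0.80–0.95.
- *m*: probability of a focus outside the prostate in a staging patient, taken as independent of *v*. Assumed 0.05–0.50.
- *b*: detection rate in recurrence patients. Section 1.2 cites 50% for PSA below 1 ng/ml and above 85% for PSA above 2 ng/ml; I use 0.50 and 0.85. Any local recurrence within *b* stays counted under both definitions below.

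**Staging patients alone**

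Any-focus rate = 1 − (1 − v)(1 − m). Rate outside the prostate = m.
- Lowest: v = 0.80, m = 0.05 gives 1 − 0.20 × 0.95 = 81.0%, against 5%.
- Highest: v = 0.95, m = 0.50 gives 1 − 0.05 × 0.50 = 97.5%, against 50%.
- With v fixed at 0.90, m = 0.05 gives 90.5% and m = 0.50 gives 95.0%. A tenfold change in extraprostatic yield moves the any-focus rate by 4.5 points.

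**Mixed stratum**

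Any focus = s[1 − (1 − v)(1 − m)] + (1 − s)b. Untreated prostate not counted = s·m + (1 − s)b. The difference is s·v·(1 − m), which does not depend on b.

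With v = 0.90, m = 0.20, b = 0.50:

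| s | Any focus | Untreated prostate not counted | Gap (points) |
|---|---|---|---|
| 0 | 50.0% | 50.0% | 0 |
| 0.1 | 54.2% | 47.0% | 7.2 |
| 0.3 | 62.6% | 41.0% | 21.6 |
| 0.5 | 71.0% | 35.0% | 36.0 |
| 0.7 | 79.4% | 29.0% | 50.4 |

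With b = 0.85 and s = 0.5 the two rates are 88.5% and 52.5%, again 36.0 points apart. At s = 0.5, with v from 0.80 to 0.95 and m from 0.10 to 0.30, the gap runs from 0.5 × 0.80 × 0.70 = 28 points to 0.5 × 0.95 × 0.90 = 42.75, about 43 points.

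**What the table shows about case mix.** With tracer performance held fixed, the any-focus column rises from 54.2% to 79.4% as s goes from 0.1 to 0.7. The other column falls from 47.0% to 29.0%. Redefining the event therefore does not remove the dependence on case mix; 3a and 3b also have to be reported separately.

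**The case against.** The strongest reply is that the opening clause of Section 8.3.1 governs the sentence: if scans are read for metastases, the foci that count are those read as metastatic. On that reading a prostate-only scan is not a detection and the bias disappears. This is a fair reading, and no section states outright that any focus, or the primary, counts. What can be shown is a numerator that permits the primary to count. Even if the narrower meaning was intended, the text has to say so, because the words naming the counted event carry no site restriction.

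A reader might also infer that the endpoint cannot show detection of metastases at all, or that the same problem arises in recurrence patients whose prostate was left in place. The documents do not support either. In 3b the original biopsy does not establish that tumour is present in a treated prostate at relapse. A focus there is a real finding: Section 1.2 treats local recurrence as an imaging target beside metastatic disease, and Section 2.1 is about tumour location generally. In 3b the open question is local recurrence versus metastasis, not a tumour known at entry. For the same reason, an endpoint restricted to extraprostatic foci in all patients would go further than the defect requires.

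Finally, the staging share, the visibility of the primary and the extraprostatic yield are all assumed. That objection stands: the direction of the bias follows from the definition, but its size does not.

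**Conclusion.** The concern holds for criterion 3a as an undefined numerator. Taken literally, Section 8.3.1 lets a biopsy-proven primary count as a detection, and no other section excludes it. Under that reading the 3a rate mainly reflects visibility of a known tumour, and the pooled PSA strata depend on an unknown mix of staging and recurrence patients.

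The illustrated ranges rest on assumed values of v and m, independence between them, and, for mixed strata, an assumed s. They show that the effect could be large, not that it is. A reader might go on to conclude that the plan's rate is inflated by a particular amount, or that its relation to PSA is flattened. Neither can be derived: the documents give no staging share and no staging-patient rates by PSA.

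**What to change.** Amend Section 8.3.1 as follows:
1. Record the local read by region, using the regions of Section 2.1's Table 1 where available.
2. In 3a, count a scan as a detection only if there is at least one focus outside the prostate.
3. In 3b, report positives confined to the prostate or prostate bed and extraprostatic positives as separate categories, so that local recurrence is still shown as a detection.
4. Report 3a and 3b separately within each PSA stratum.

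This needs a paragraph of text and a region field on the existing local read, with no extra scan, reader or patient.

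There are three costs. The headline rate in 3a will be lower than an any-focus rate. Strata become smaller: for a rate of 50%, the 95% half-width 1.96 × √(0.25/n) is 3.1 points at n = 1,000, 4.4 at n = 500 and 6.9 at n = 200. And since Section 1.1 says the endpoints were aligned for multi-institution pooling, the sponsor should check that the new definition stays compatible with the pooled data; recording by region should allow another definition to be derived alongside it.

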9.1 Pre-study Documentation

This study will be conducted in accordance with the ethical principles that have their origin in the Declaration of Helsinki as stated in 21 CFR §312.120(c)(4); consistent with GCP and all applicable regulatory requirements.

Before initiating this trial, the Investigator will have written and dated approval from the Institutional Review Board for the protocol, written informed consent form, subject recruitment materials, and any other written information to be provided to subjects before any protocol related procedures are performed on any subjects.

The clinical investigation will not begin until either FDA has determined that the study under the Investigational Drug Application (IND) is allowed to proceed or the Investigator has received a letter from FDA stating that the study is exempt from IND requirements.

9.2 Institutional Review Board Approval

The protocol, the proposed informed consent form, and all forms of participant information related to the study (e.g. advertisements used to recruit participants) will be reviewed and approved by the UCSF CHR (UCSF Institutional Review Board). Prior to obtaining CHR approval, the protocol must be approved by the Helen Diller Family Comprehensive Cancer Center Site Committee and by the Protocol Review Committee (PRC). The initial protocol and all protocol amendments must be approved by the IRB prior to implementation.

9.3 Informed Consent

All participants must be provided a consent form describing the study with sufficient information for each participant to make an informed decision regarding their participation. Participants must sign the CHR-approved informed consent form prior to participation in any study specific procedure. The participant must receive a copy of the signed and dated consent document. The original signed copy of the consent document must be retained in the medical record or research file.

9.4 Changes in the Protocol

Once the protocol has been approved by the UCSF CHR, any changes to the protocol must be documented in the form of an amendment. The amendment must be signed by the Investigator and approved by PRC and the CHR prior to implementation.

If it becomes necessary to alter the protocol to eliminate an immediate hazard to patients, an amendment may be implemented prior to CHR approval. In this circumstance, however, the Investigator must then notify the CHR in writing within five (5) working days after implementation. The Study Chair and the UCSF study team will be responsible for updating any participating sites.

10 Protection of Human Subjects

Appendix 1 Schedule of Study Procedures and Assessments

	Screening (Day -90 to Day 1)	Imaging (Day 1)
Informed Consent	X	
Inclusion/Exclusion Criteria Assessment	X	
PSA	X	
⁶⁸ Ga-PSMA-11 Administration		X
Imaging (PET/CT or PET/MRI)		X
Adverse Event Collection		X
